1.2. Schema

Figure 1: Schema Detailing IMP Treatment and Assessments for Trial ARGX-113-1904

ABQOL=Autoimmune Bullous Disease Quality of Life; CR=complete clinical remission; CRmin=complete remission on minimal therapy; DC=disease control; Efg=efgartigimod PH20 SC; EoS=end of consolidation; EoS=end of study; EQ-5D-5L=EuroQol 5-dimension 5-level; GTI=Glucocorticoid Toxicity Index; OLE=open-label extension; PD=pharmacodynamics; PDAI=Pemphigus Disease Area Index; PF=pemphigus foliaceus; PK=pharmacokinetics; PV=pemphigus vulgaris; SC=subcutaneous.

1.3. Schedule of Activities

The schedule of activities is applicable globally, except for China. The China-specific Schedule of Activities is provided in Section 10.16.1.1.

Table 1: Schedule of Activities for Trial ARGX-113-1904

Trial Period	Screening ^g	Treatment						EoS/ED ^a	Follow-up	
		V1 (BL)	V2	Observational visits	IMP admin only visit	Observational visits	On-site visits every 4 weeks after CRmin until W31		Follow-up W34	Follow-up W38 ^c
Visit Number				Weekly on-site visits until CR ^c	Weekly home or on-site visits until CRmin ^d	On-site visits every 4 weeks until CRmin	On-site visits every 4 weeks after CRmin until W31	W31	EoS/ED +3W	EoS/ED +7W
Trial Day/Week	D-21 to D-1	D1 (W1)	D8 (W2)	D15 (W3) until CR	CR until CRmin	CR until CRmin	CRmin until W31	W31		
Visit Window		±0 days	±2 days ^f		V1 + 7× ±2 days ^f			±2 days ^f	±3 days ^f	
Assessment/Procedure										
Informed consent ^e	X									
Inclusion/exclusion criteria	X	X								
DIF/histopathology ^h	X									
Concomitant therapies/procedures	X								Continuous monitoring	
Karnofsky performance score	X									
Demography	X									
Height and weight ⁱ	X			X ⁱ		X ⁱ	X ⁱ	X		

Trial Period	Visit Number	Trial Day/Week	Visit Window	Screening	Treatment						EoS/ED ^a	Follow-up	
					V1 (BL)	V2	Observational visits	IMP admin only visit	Observational visits	EoS/ED +3W		Follow-up W34	Follow-up W38 ^c
		D1 (W1)	D8 (W2)	D15 (W3) until CR	Weekly on-site visits until CR ^c	Weekly home or on-site visits until CRmin ^d	On-site visits every 4 weeks until CRmin	On-site visits every 4 weeks after CRmin until W31	W31	±2 days ^f	EoS/ED +3W	Follow-up W34	Follow-up W38 ^c
		±0 days	±2 days ^f			V1 + 7× ±2 days ^f	CR until CRmin	CR until CRmin	W31		±3 days ^f	EoS/ED +7W	
Physical examination and vital signs ^{h,k}		X	X	X			X	X	X	X	X	X	X
ECG ^j		X		X ^l			X ^l		X				
Medical and surgical history		X											
Randomization ^m				X									
Urinalysis ^{n,o}		X	X	X			X	X	X	X ^b	X	X	X
Urine pregnancy test ^p		X		X ^p			X	X	X	X ^b	X	X	X
Blood sampling:													
Active viral infection test ^q		X											
Serum pregnancy test ^r		X											
Clinical chemistry & hematology ^{s,o,s}		X	X	X			X	X	X	X ^b	X	X	X

Trial Period	Visit Number	Trial Day/Week	Visit Window	Screening	Treatment						EoS/ ED ^a	Follow-up	
					V1 (BL)	V2	Observational visits	IMP admin only visit	Observational visits	EoS/ED +3W		Follow-up W34	Follow-up W38 ^c
		D1 (W1)	±0 days		Weekly on-site visits until CR ^c	Weekly home or on-site visits until CRmin ^d	On-site visits every 4 weeks until CRmin	On-site visits every 4 weeks after CRmin until W31	W31	EoS/ED +3W	Follow-up W34	Follow-up W38 ^c	
		D8 (W2)	±2 days ^f		D15 (W3) until CR	CR until CRmin	CR until CRmin	CRmin until W31	W31	EoS/ED +3W	EoS/ED +3W	EoS/ED +7W	
					V1 + 7× ±2 days ^f						±2 days ^f		
Anti-Dsg-1 and anti-Dsg-3 antibodies ^{j,o}		X	X	X	X		X	X	X	X	X ^b	X	
PK ^{j,o,t}		X	X ^t		X		X	X	X	X	X ^{b,t}	X	
Total IgG and IgG subtypes ^{j,o,u}		X	X	X	X		X	X	X	X	X ^b	X	
Vaccination antibodies ^{j,o,v}		X	X	X	X		X	X	X	X	X ^b	X	
Anti-drug antibodies ^{j,w}		X			X (every 2 weeks)		X	X	X	X		X	
IgG autoantibody subtypes/specificity and cytokines ^{j,x}		X			X ^x		X	X	X	X	X ^b	X	
B- and T-cell populations ⁱ		X			X ^y				X	X			
RNA transcriptional profile ⁱ		X			X ^y				X	X			

Trial Period	Screening		Treatment					EoS/ED ^a		Follow-up	
	V1 (BL)	V2	Observational visits	IMP admin only visit	Observational visits		Follow-up W34	Follow-up W38 ^c			
Visit Number			Weekly on-site visits until CR ^c	Weekly home or on-site visits until CRmin ^d	On-site visits every 4 weeks until CRmin	On-site visits every 4 weeks after CRmin until W31	W31		EoS/ED +3W	EoS/ED +7W	
Trial Day/Week	D1 (W1)	D8 (W2)	D15 (W3) until CR	CR until CRmin	CR until CRmin	CRmin until W31	W31				
Visit Window	±0 days	±2 days ^f		V1 + 7× ±2 days ^f			±2 days ^f		±3 days ^f		
HLA/non-HLA genotyping ^j	X		X ^z								
Substudies:											
Skin biopsies (at selected sites) ^{j,aa}	X		X ^{aa}				X ^{aa}				
Photography (at selected sites) ^{j,bb}	X	X ^{bb}	X ^{bb}					X ^{bbb}			
QoL Assessments:											
EQ-5D-5L ^{j,cc}	X		X ^{dd}		X ^{dd}	X ^{dd}	X				
ABQOL ^{j,cc}	X		X ^{dd}		X ^{dd}	X ^{dd}	X				
GTP ^j	X		X ^{ee}		X ^{ee}	X ^{ee}	X				
IMP self-administration training ^{ff}			X		X						
IMP administration ^{gg}	X (■■■ mg)	X (■■■ mg)	X	X	X			X ^b			
PDAP ^j	X	X	X		X	X	X	X	X	X	

Trial Period	Screening		Treatment				EoS/ ED ^a	Follow-up	
	V1 (BL)	V2	Observational visits	IMP admin only visit	Observational visits	Follow-up W34		Follow-up W38 ^c	
Visit Number			Weekly on-site visits until CR ^c	Weekly home or on-site visits until CRmin ^d	On-site visits every 4 weeks until CRmin	On-site visits every 4 weeks after CRmin until W31	W31	EoS/ED +3W	EoS/ED +7W
Trial Day/Week	D1 (W1)	D8 (W2)	D15 (W3) until CR	CR until CRmin	CR until CRmin	CRmin until W31	W31		
Visit Window	±0 days	±2 days ^f		V1 + 7 × ±2 days ^f			±2 days ^f		±3 days ^f
Disease assessment ^{hh}		X	X		X	X	X	X	X
Prednisone taper ⁱⁱ			X	X	X	X	X	X	X
AE monitoring	Continuous monitoring								

ABQOL=Autoimmune Bullous Disease Quality of Life; admin=administration; BL=baseline; BMI=body mass index; CR=complete clinical remission; CRmin=CR on minimal therapy; D=day; DC=disease control; DIF=direct immunofluorescence; Dsg=desmoglein; ECG=electrocardiogram; ED=early discontinuation; EoC=end of consolidation; EoS=end of study; FSH=follicle-stimulating hormone; GTI=Glucocorticoid Toxicity Index; HLA=human leukocyte antigen; IgG=immunoglobulin G; ICF=informed consent form; IMP=investigational medicinal product; OLE=open-label extension; PDAI=Pemphigus Disease Area Index; PK=pharmacokinetics; RBC=red blood cells; UNS=unscheduled visit; WBC=white blood cells; W=week; V=visit

^a All participants will complete EoS/ED, which will be the end of the trial for participants who enroll in the OLE trial ARGX-113-1905. Participants who do not enroll in the OLE trial ARGX 113 1905 will complete the follow-up visits at W34 and W38.

^b In case of suspected new lesions as reported by the participants, AEs, flare or other safety reasons, participants should come to the clinic. This may require an unscheduled visit. Depending on the reason for the visit, different assessments need to be performed. See Section 8 for more information. Participants with new lesions or flare after achieving CR should return to weekly on-site visits until CR is achieved again.

^c A minimum of 6 on-site visits, V1(BL)/W1 to W6, are required before switching to home administrations, even if CR is achieved earlier than W6. The W7 visit is the first eligible “IMP administration only” visit (refer to column “Weekly home or on-site visits until CRmin”), at home or on-site, if CR is achieved between W1 and W6.

^d Home visits are allowed once participants achieve CR, but not before W7. The investigator should call the participant every 2 weeks until CRmin is achieved to confirm the participant is still in CR. On-site visits may continue at the investigator’s discretion.

^e W38 (follow-up visit 2) is the end of the trial for participants who do not enroll in the OLE trial ARGX-113-1905. The W38 follow-up visit will only be required for those participants who were still receiving IMP at least once from W27 onward. For participants who ended treatment prior to W27, W34 will be the end of the trial.

^f Trial visit windows are ±2 days during the treatment period and ±3 days for follow-up visits.

- ^g No trial-related assessments can be initiated before the participant has provided a signed ICF.
- ^h Only required if not available from medical history.
- ⁱ Height and weight will be measured (and BMI will be calculated accordingly) at screening, at week W15 (or the next on-site visit if W15 does not coincide with an on-site visit), and EoS/ED. Weight will also be measured if there has been an obvious change since the last measurement.
- ^j At visits in which IMP is administered, the assessment or procedure should be completed before dosing.
- ^k A complete physical examination will be completed at each on-site visit. Vital sign measurements include systolic and diastolic blood pressure, heart rate, and body temperature. Supine blood pressure and heart rate will be measured using standard equipment after at least 10 minutes rest.
- ^l ECG to be taken at W12. If the W12 visit does not coincide with an on-site visit, then the assessment should be performed at the next on-site visit. ECG (heart rate, PR, QT, and QRS interval) will be read centrally. QTcF and QTcB will be calculated.
- ^m Randomization will take place on day 1 after all eligibility checks are confirmed (eg, PDAI) and before other baseline assessments are run, and prior to dosing.
- ⁿ Urinalysis will be performed by dipstick method and will include specific gravity, pH, protein, glucose, ketones, blood, bilirubin, urobilinogen, nitrite, leukocyte esterase, and microscopic examination (if blood or protein test results are abnormal).
- ^o Samples will be taken every week from V1(BL)/W1 to W9 and then every 4 weeks and at the visit where CR is observed. Once CR is achieved, samples will be taken every 4 weeks at on-site visits until EoS/ED. For participants achieving CR between V1(BL)/W1 and W6, samples will be taken weekly from W1 to W6 and then every 4 weeks at on-site visits until EoS/ED.
- ^p A urine pregnancy test will be conducted and analyzed locally during on-site visits at least once every 4 weeks (before and after CR) and at the time of CR.
- ^q Viral testing for hepatitis B surface antigen (HBsAg), hepatitis B surface antibody (anti-HBs), hepatitis B core antibody (anti-HBc), hepatitis B virus (HBV) DNA, hepatitis C virus (HCV) antibodies, HCV messenger RNA (mRNA), and human immunodeficiency virus (HIV) antibodies.
- ^r At screening, a serum pregnancy test must be performed in women of childbearing potential or FSH test to confirm postmenopausal status.
- ^s Clinical blood laboratory tests will include hematology and blood chemistry at all visits and international normalized ratio (INR) or activated partial thromboplastin time (aPTT) at screening only. The hematology profile includes hemoglobin, hematocrit, mean corpuscular volume (MCV), RBC count, platelet count, WBC count with differential. The blood chemistry profile includes sodium, potassium, calcium, hemoglobin A1c (HbA1c), creatinine, creatinine clearance, blood urea nitrogen (BUN), alanine aminotransferase (ALT), aspartate aminotransferase (AST), total bilirubin, gamma-glutamyl transferase (GGT), C-reactive protein (CRP), alkaline phosphatase (ALP), lactate dehydrogenase (LDH), low-density lipoprotein cholesterol (LDL-C), high-density lipoprotein cholesterol (HDL-C), total cholesterol, triglycerides, uric acid, total protein, and albumin.
- ^t For PK assessment, blood samples will be taken predose (within 2 hours before the start of IMP administration at visits where IMP is administered). An additional PK sample will be taken on D3 and on D11 (\pm 1 day) until samples from 24 participants are obtained. At unscheduled visits blood samples for PK will only be taken if IMP is administered.
- ^u At screening, total IgG will be measured as part of inclusion and exclusion criteria. The pharmacodynamic (PD) biomarkers total IgG and its subtypes (IgG1, IgG2, IgG3, and IgG4) will be measured centrally from a blood sample taken predose.
- ^v An extra sample(s) will be taken for additional research (including vaccination antibodies and other additional research). The actual testing of vaccination antibodies depends on (a) whether a vaccination was given to the participant; (b) whether a test is available for the vaccination given to the participant; and (c) whether the sample requirements (serum, volume, frozen sample, storage duration) match the serum samples taken and reserved for this. Timepoints for analysis will be decided upon occurrence of vaccination during the study.
- ^w Anti-drug antibodies to efgartigimod (in serum samples) and antibodies against rHuPH20 (in plasma samples) will be tested predose every 2 weeks from V1(BL)/W1 to W9 and then every 4 weeks at on-site visits and at the visit where CR is observed. Once CR is achieved, samples will be taken every 4 weeks at on-site visits until EoS/ED. For participants achieving CR between V1(BL)/W1 and W6, samples will be taken predose at V1(BL)/W1, W3, W5, the visit

where CR is observed, W10, and then every 4 weeks at on-site visits until EoS/ED. Neutralizing antibodies (Nab) will be tested for all confirmed positive ADA samples.

^x Blood sampling for IgG autoantibody subtypes and specificity will be taken every 4 weeks (V1[BL]/W1, W5, W9, etc) and at the visit where CR is observed. Once CR is achieved, samples will be taken every 4 weeks at on-site visits until EoS/ED. For participants achieving CR between V1(BL)/W1 and W6, samples will be taken at V1(BL)/W1, W5, the visit where CR is observed, W10, and then every 4 weeks at on-site visits until EoS/ED. Serum aliquots from all time points will be used for IgG subtype and specificity analyses. For cytokines and complementary specificity analyses, aliquots from baseline, after 4 weeks (W5), W13 (or the visit at which CR is observed if before W13), and EoS/ED will be used.

^y Samples for B- and T-cell populations and RNA transcriptional profiles will be performed at baseline, after 4 weeks (W5) and at W13 (or the visit at which CR is observed if before W13) and at EoS/ED.

^z HLA/non-HLA genotyping will be performed at baseline and D15.

^{aa} Two 4 mm skin biopsies, 1 peri-lesional and 1 non-lesional, will be collected solely based on voluntary participation at baseline and after healing of 80% of blisters (EoC) or at EoS/ED (in case EoC has not been achieved) for scientific purposes.

^{bb} Pictures of different anatomical regions may be taken per judgment of the investigator. As a guidance, time points of baseline, DC, CR and flare are indicated. Pictures may also be taken at intermediate timepoints.

^{cc} Questionnaires are to be completed prior to any other activity.

^{dd} Assessments will be performed at baseline, after 4 weeks (W5), W15, and EoS/ED visits. If the W15 visit does not coincide with an on-site visit, then the assessment should be performed at the next on-site visit.

^{ee} The GTI assessment will be performed only at baseline, W15 and EoS/ED. If W15 does not coincide with an on-site visit, then the assessment should be performed at the next on-site visit.

^{ff} Participants will be trained to self-administer IMP (foreseen in the OLE trial; not in the ARGX-113-1904 trial) during the first 4 visits as of V3 when IMP is administered; thereafter, training for self-administration is optional (only if needed).

^{gg} IMP will be administered until CRmin. To ensure proper safety monitoring, participants should remain at the site for at least 1 hour after the first administration and for 15 minutes after subsequent administrations. Participants will be released according to their clinical status. For Germany-specific monitoring instructions, refer to Section 10.16.2.1. Participants who experience treatment failure, or flare after achieving CRmin, will be allowed to roll over into the OLE trial ARGX-113-1905 earlier than W31. Participants who do not roll over into trial ARGX-113-1905 will complete the treatment-free follow-up period.

^{hh} Disease assessment parameters include disease control (DC), end of consolidation (EoC), complete clinical remission (CR), complete remission on minimal therapy (CRmin), complete remission off therapy (CRoff), flare, and treatment failure. Participants who have achieved CR and have new lesions should come to the clinic for a UNS for disease assessment.

ⁱⁱ Prednisone dose tapering will begin 2 weeks after achieving CR or 4 weeks after sustained EoC (thus, no new lesions have developed for a minimum of 6 weeks and approximately 80% or more of lesions have healed).

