- Moderate to severe (PDAI activity score ≥ 15), experiencing flare, and off prednisone therapy \pm a conventional immunosuppressant (eg, azathioprine, cyclophosphamide, methotrexate, mycophenolate mofetil) or dapsone. Note: conventional immunosuppressants and dapsone must be discontinued before baseline.
- Moderate to severe (PDAI activity score ≥ 15), experiencing flare, while receiving a tapered dose of oral prednisone (or equivalent), provided that prednisone (or equivalent) has been given at stable dose \pm a conventional immunosuppressant (eg, azathioprine, cyclophosphamide, methotrexate, mycophenolate mofetil) or dapsone and participants are fit to start prednisone treatment at 0.5 mg/kg qd at baseline. Note: conventional immunosuppressants and dapsone must be discontinued before baseline.

The trial comprises a screening period of up to 3 weeks, a treatment period of up to 30 weeks, and an 8-week follow-up period for participants who do not enroll into the open-label extension (OLE) trial ARGX-113-1905.

After confirmation of eligibility, participants will be randomized in a 2:1 ratio to receive efgartigimod PH20 SC or placebo, as follows:

- Efgartigimod PH20 SC will be administered by SC injection on day 1 and day 8 at a dose of [REDACTED] mg, followed by weekly administrations of 1000 mg until CRmin is observed. Efgartigimod PH20 SC will be administered at on-site visits until CR, with a minimum of 6 weekly on-site visits (W1 to W6). After achieving CR, efgartigimod PH20 SC will be administered at on-site visits or at home by a nurse until CRmin is achieved.

- Placebo (vehicle with 2000 U/mL of rHuPH20) SC will be administered using the same regimen.

All participants or their caregivers will be invited to receive training for future self-administration of efgartigimod PH20 SC in the OLE trial ARGX-113-1905. The caregiver is a person of legal age that the participant proposes to perform the administrations. If the participants or caregivers have successfully completed self-administration training to the satisfaction of authorized staff, then the participants or caregivers may self-administer the next injections at the site under supervision of authorized staff.

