4. TRIAL DESIGN

4.1. Overall Design

This is a prospective, multicenter, randomized, double-blinded, placebo-controlled trial to investigate the efficacy, safety, patient outcome measures, tolerability, immunogenicity, PK, and PD of efgartigimod PH20 SC in adult participants aged from 18 years with PV or PF. See Section 1.2 for a diagram of the trial design. Enrolled participants are those who are either newly diagnosed or experiencing flare as follows:

- Moderate to severe (PDAI activity score ≥ 15) newly diagnosed and naïve to treatment.
- Moderate to severe (PDAI activity score ≥ 15) newly diagnosed while receiving a first course of oral prednisone (or equivalent). According to clinical judgment, the participant has shown no significant improvement of PV or PF signs for at least 2 weeks before baseline and is considered fit to start prednisone treatment at 0.5 mg/kg daily (qd) at baseline.
- Moderate to severe (PDAI activity score ≥ 15), experiencing flare, and off prednisone therapy \pm a conventional immunosuppressant (eg, azathioprine, cyclophosphamide, methotrexate, mycophenolate mofetil) or dapsone. Note: conventional immunosuppressants and dapsone must be discontinued before baseline.
- Moderate to severe (PDAI activity score ≥ 15), experiencing flare, while receiving a tapered dose of oral prednisone (or equivalent), provided that prednisone (or equivalent) has been given at stable dose \pm a conventional immunosuppressant (eg, azathioprine, cyclophosphamide, methotrexate, mycophenolate mofetil) or dapsone and participants are fit to start prednisone treatment at 0.5 mg/kg qd at baseline. Note: conventional immunosuppressants and dapsone must be discontinued before baseline.

The trial comprises a screening period of up to 3 weeks, a treatment period of up to 30 weeks, and an 8-week follow-up period for participants who do not enroll into the OLE trial ARGX-113-1905.

After confirmation of eligibility, participants will be randomized in a 2:1 ratio to receive efgartigimod PH20 SC or placebo, as follows:

- Efgartigimod PH20 SC will be administered by SC injection on day 1 and day 8 at a dose of [REDACTED] mg, followed by weekly SC administrations of 1000 mg until CRmin is observed. Efgartigimod PH20 SC will be administered at on-site visits until CR. After achieving CR, efgartigimod PH20 SC will be administered at on-site visits or at home by a nurse until CRmin is achieved.

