6.6. Continued Access to Study Intervention After the End of the Trial

Efgartigimod PH20 SC or placebo SC will be administered subcutaneously until CRmin. Participants at the EoS visit or ED visit in trial ARGX-113-1904 will be given the option to enroll into the OLE trial ARGX-113-1905 after confirmation of eligibility, while retaining the blinding of trial ARGX-113-1904. For each participant, the date of the baseline visit in the OLE trial ARGX-113-1905 will be the same as the date of the EoS visit in trial ARGX-113-1904. There is no need to schedule an additional visit for a roll over visit. At baseline of the OLE study, participants will be treated according to their clinical status at entry of the OLE trial ARGX-113-1905, as defined in the trial protocol.

Week 34 (follow-up visit 1) or week 38 (follow-up visit 2) is the EoS for participants who do not enroll in the OLE trial ARGX-113-1905. The week 38 follow-up visit will only be required for those participants who were still receiving IMP at least 1 visit between week 26 and EoS/ED. For participants who ended treatment prior to week 26, week 34 will be the EoS visit.

If a participant withdraws/discontinues early and does not roll over to the OLE trial (ARGX-113-1905), usual treatment will be administered, if required, in accordance with the trial site's standard of care and generally accepted medical practice depending on the participant's individual needs. Depending on the clinical status of the participant and the clinical judgment from the investigator, completion of the treatment-free follow-up period may be performed.

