Participants who experience treatment failure, or flare after achieving CRmin, will be allowed to roll over into the OLE study ARGX-113-1905 earlier than week 30. Participants who do not roll over into study ARGX-113-1905 will complete an 8-week treatment-free follow-up period. Participants experiencing an SAE related to prednisone in ARGX-113-1904 are considered treatment failures and may also benefit from an early roll over to the OLE, according to clinical judgment of the investigators.

	Statistical Analysis Plan	
ARGX-113-1904	Final analysis	Final 2.0 of 22NOV2023

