2.2 PHASES AND TIME POINTS

2.2.1 Analysis Phases and Periods

All events and assessments will be allocated to phases and periods as defined below.

Table 1: Phase definition

Phase	Period	Start	End
Screening		Date of signing the informed consent form (ICF), with 00:00 added as time part ^a	First IMP administration date/time – 1 minute
Treatment	On Treatment	First IMP administration date/time	Last IMP administration date with 23:59 added as time part.
	Off Treatment	End of on treatment period + 1 minute	For participants who roll over to study 1905, date of study termination (of study 1904), with 23:59 added as time part. For participants who do not roll over to study 1905, date of end of study/early discontinuation visit ^b , with 23:59 added as time part. For participants who do not roll over to study 1905 and have no end of study/early discontinuation visit, date of treatment discontinuation (of study 1904), with 23:59 added as time part.
Following phase is only applicable for participants in the treatment phase who do not roll over to study 1905.			
Follow-up		End of treatment phase + 1 minute	Date of study termination (of study 1904), with 23:59 added as time part.

^a For rescreened participants without new IC signed the rescreening visit date is used as start of screening phase

^b Treatment phase lasts until EoS/ED also if a participant may be off treatment after CRmin

Per definition and for each participant, the first phase starts on the date of the earliest available ICF signature, and the last available phase ends on the date of study termination with 23:59 added as time part.

Adverse events and concomitant medications will be allocated to phases (AE's also to periods) as described in sections 5.1.2 and 3.4.2 respectively. All other assessments will be allocated to phases based on the assessment date/time.

A set of subperiods will be derived within the treatment phase, to support the analysis of treatment-emergent adverse events (TEAEs) versus post-TEAEs, as defined in Table 2 below.

Table 2: Subperiod definition for AE

Subperiod	Start	End
Treatment emergent 1	Treatment period start date/time (see Table 1)	Date of first EFG where the next EFG is at least 61 days later + 60 days ^a
Post-treatment emergent 1	End date/time of previous subperiod + 1 minute	Start date/time of next subperiod - 1 minute

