5. SAFETY ANALYSES

5.1 ADVERSE EVENTS

5.1.1 *Available data*

Adverse events (AEs) are coded into SOC and PT using the latest version of the MedDRA available at the moment of the database lock. For each AE, start and stop date/times are collected as well as severity (NCI CTCAE v5.0), a seriousness flag, treatment relatedness, relatedness to procedures, action taken towards the IMP, outcome, and AE of special interest (AESI) category (infection).

5.1.2 *Derivation rules*

Treatment-emergent adverse events (TEAE) are defined as AEs starting on or after first administration of any IMP up through 60 days after the last administration of the IMP prior to the AE. Post-TEAEs are AEs starting after first administration of IMP that are not TEAEs.

Based on their start date/time, AEs will be allocated to the phase during which they started. Each AE will therefore be reported in only one phase. In case the AE start date/time is incomplete or missing and the AE could consequently be allocated to more than one phase, a worst-case allocation will be done as detailed below:

- Treatment phase vs. non-treatment phase: the AE will be allocated to the treatment phase unless the available parts of the AE start or stop date/time provide evidence for allocating to the non-treatment phase.

A death case is defined as an AE with outcome ‘fatal’.

An AE for which the IMP was discontinued is defined as an AE with action taken ‘drug withdrawn’.

Treatment relatedness will be dichotomized as follows in tables:

- Treatment related: related, probably related, possibly related or missing
- Not treatment related: not related, unlikely related

Adverse events of special interest will be defined using MedDRA system organ class ‘Infections and infestations’.

Injection-related reactions (IRRs) will be defined as all AEs with MedDRA preferred terms that are listed in either:

- Hypersensitivity standardized MedDRA query (SMQ) (broad selection)
- Anaphylactic reaction (SMQ) (broad selection)
- Extravasation events (injections, infusions and implants) (SMQ) (broad selection), excluding implants

AND occurring within 48 hours of an administration, or within 2 days in case no AE start time is available. In case of (partially) missing AE start date, the AE will be considered as an IRR, unless the available parts of the AE start date provide evidence it did not occur within 48 hours of an injection.

	Statistical Analysis Plan	
ARGX-113-1904	Final analysis	Final 2.0 of 22NOV2023

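### Follow-up visit 2 is waived by study week although follow-up is timed from each participant's own EoS/ED, so some early leavers have their last scheduled visit 21 to 49 days after the last dose

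*Protocol*

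**What the plan says.** **Timing of the visits.** Protocol Table 1 (Section 1.3) places follow-up visit 1 at EoS/ED plus 3 weeks and visit 2 at EoS/ED plus 7 weeks, under the column labels W34 and W38. The SAP does the same. In SAP 2.2.1 the treatment phase of someone who does not roll over ends at the "date of end of study/early discontinuation visit". SAP 2.2.4 then sets follow-up targets at days 21 and 49 from there.

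**Who needs visit 2.** Three texts differ:
- Table 1 footnote a is unqualified: "Participants who do not enroll in the OLE trial ARGX 113 1905 will complete the follow-up visits at W34 and W38".
- Table 1 footnote e requires visit 2 only if IMP was still being given from W27. Otherwise: "For participants who ended treatment prior to W27, W34 will be the end of the trial". It is repeated in Tables 10, 16 and 18 and in SAP 9.5.
- Section 6.6 moves the cut-off by a week: "For participants who ended treatment prior to week 26, week 34 will be the EoS visit".

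**Length of follow-up.** The synopsis describes "an 8-week follow-up period for participants who do not enroll into the open-label extension (OLE) trial ARGX-113-1905", Section 4.1 describes "an 8-week follow-up period for participants who do not enroll into the OLE trial ARGX-113-1905", and SAP 1.2 states "Participants who do not roll over into study ARGX-113-1905 will complete an 8-week treatment-free follow-up period". The duration line in the synopsis is weaker. It counts from the last dose and gives 8 weeks as a maximum.

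**Safety definition.** SAP 5.1.2 treats an adverse event as treatment-emergent "up through 60 days after the last administration of the IMP prior to the AE".

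**The concern.** The waiver runs on the study calendar and the visits run on the participant's own clock. The two agree when EoS is at W31. When someone leaves early, the waiver still applies, but visit 1 has moved forward with the ED visit, so the last scheduled contact can come only a few weeks after the last dose.

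Those affected stopped early, some of them because of an adverse event. Once participation ends, Section 8.4.1 does not oblige investigators to look for new events. What would be missed is mainly new non-serious events, including infections, which Section 8.4.8 makes the adverse event of special interest because the drug lowers IgG.

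**Working it through.** **Inputs.** Visit 1 = EoS/ED + 21 days and visit 2 = EoS/ED + 49 days (Table 1; SAP 2.2.4). Visit 2 is required if the last dose is at or after W27 (footnote e) or week 26 (Section 6.6). Windows are ±2 days on treatment and ±3 days in follow-up (footnote f). The treatment-emergent window is 60 days (SAP 5.1.2). Nominal day of week w = 1 + 7(w − 1).

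**Reproducing the plan's 8 weeks.** With EoS at W31 (day 211), visit 1 is day 232 (W34) and visit 2 is day 260 (W38).
- Last dose W26 (day 176), visit 1 only: 232 − 176 = 56 days.
- Last dose W27 (day 183), visit 2 required: 260 − 183 = 77 days.
- Last dose W30 (day 204), visit 2 required: 260 − 204 = 56 days.

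So the W27 cut-off never gives less than 56 days when EoS is at W31.

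**Early EoS/ED.** Let k be the weeks from last dose to EoS/ED. For a last dose before W27 the last scheduled visit is 21 + 7k days after that dose. With visit 2 kept it would be 49 + 7k.

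| k | Footnote e (days) | Shortfall against 56 | Visit 2 kept (days) |
|---|---|---|---|
| 0 | 21 | 35 | 49 |
| 1 | 28 | 28 | 56 |
| 2 | 35 | 21 | 63 |
| 3 | 42 | 14 | 70 |
| 4 | 49 | 7 | 77 |
| 5 | 56 | 0 | not needed |

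The waiver removes 49 − 21 = 28 days in every row from k=0 to k=4. At k=0, 7 of the 35 days come from the 7-week schedule itself. Participants who stop at CRmin and have EoS/ED 5 or more weeks later already reach 56 days.

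**Windows.** At k=0: 21 ± 3 = 18 to 24 days. At k=1, with every window at its limit: (7 ± 4) + (21 ± 3) = 21 to 35 days. Windows do not close the gap.

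**Coverage of the 60-day window.** Footnote e: 21/60 = 35% (k=0) and 28/60 = 47% (k=1). With visit 2: 49/60 = 82% and 56/60 = 93%.

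**The two cut-offs.** For a last dose at W26 and ED at W27 (day 183), footnote e ends at visit 1, day 204: 204 − 176 = 28 days. Section 6.6 requires visit 2, day 232: 232 − 176 = 56 days.

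**The case against.** A reader might infer that the plan promises everyone 8 weeks after the last dose and then breaks that promise. The documents do not support this. The only general statement anchored to the last dose is the synopsis duration line, and it sets a ceiling. The other texts name an 8-week period without saying that it starts at the last dose. Section 6.6 also leaves completion of follow-up after early withdrawal without rollover to the investigator's judgment, and Section 7.2 only offers entry. These are real limits. Against them, Sections 7.1 and 8 direct discontinuers who do not roll over into follow-up, and for those who enter, the only fixed length comes from the conflicting cut-offs.

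Another defence is that W34 means calendar week 34, which would always give at least 56 days. The EoS/ED +3W row, Section 6.6's own label of follow-up visit 1, and the SAP windows all point the other way.

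The safety loss is also partly covered. Known events are followed to resolution (8.4.3). Related SAEs that come to the investigator's attention are reported (8.4.1). SAEs spontaneously reported within 30 days of the last visit are collected (8.4.4), which reaches day 51 at k=0 (21 + 30) and day 58 at k=1 (28 + 30). Unblinded participants have their own 8 weeks (6.3.1). The 60-day window is a classification rule, not a follow-up standard: a completer with last dose at W30 has 56 days. Rates per participant-year use actual period durations, so their denominators shorten too. All of this stands, and it narrows the loss to active collection of mainly new non-serious events.

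A reader might also infer a threat to efficacy. SAP 4.1.2 does consider follow-up visits when defining responses, so a dropped visit could in principle be one fewer chance to record one. The documents give no basis for calling that an effect on the efficacy results: the rule is the same in both arms, and the primary test and its level do not change.

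**Conclusion.** The point holds as a minor correction to the safety schedule. The study-week waiver does not fit visits timed from EoS/ED, and its two versions conflict for a last dose at W26. For a participant who does not roll over, enters follow-up, had the last dose before W27 and has EoS/ED less than 5 weeks later, scheduled follow-up ends 21 to 49 days after that dose, typically 28. The waiver costs 28 days of active collection in each such case.

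This rests on nominal visit weeks and on reading W34 as EoS/ED plus 3 weeks. The 21-day figure needs ED in the same week as a dose, for example after an acute reaction, and is the extreme. The documents give no rate of early leavers who decline the extension. Since SAP 1.3 makes every randomized participant eligible for it, the group is probably small. Type I error and power are not affected.

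**What to change.** In footnote e (Tables 1, 10, 16 and 18; SAP 9.5) and in Section 6.6, replace both week cut-offs with one rule: participants who do not enter the extension need follow-up visit 2 (EoS/ED plus 7 weeks) unless EoS/ED is at least 5 nominal weeks after the last IMP dose, in which case visit 1 is the end of the trial. Where EoS/ED is in the same week as the last dose, time visit 2, or an adverse event contact, at last dose plus 8 weeks; visit 2 at its usual time would reach only 49 days. Align footnote a. State in Section 6.6 that the rule sets the length of follow-up for those who enter it, while participants may still decline under Section 7.2.

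Everyone with EoS at W31 keeps footnote e's present schedule. Compared with Section 6.6, a W26 last dose with EoS at W31 would no longer need visit 2, because visit 1 is already at 56 days.

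The cost is a wording amendment and one already-defined visit for a few early leavers. For k = 2 to 4 that visit falls 63 to 77 days after the last dose, beyond 8 weeks, but footnote e already gives 77 days to a W27 last dose with EoS at W31.
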